The optimal frequency, duration and number of tDCS sessions to maximize effects on craving, or any other construct in this young field, remain obscure. We chose to deliver 5 sessions of tDCS because this number has been used in prior successful tDCS craving interventions and must be balanced against adherence concerns. While we are hopeful that participants will complete 5 consecutive days of tDCS, the interruption of weekends and the transition from the ADP setting (where the tDCS protocol will start) where days are structured, to the community setting, raises the possibility of missed tDCS sessions and therefore we will allow these 5 sessions to occur over 10 days if necessary, as has been described in prior studies, tracking both average number of sessions received and period of treatment for analyses. The sham tDCS condition is included in our design to separate the effects of ongoing opioid treatment from the effect of active tDCS on craving. We decided not to include a third no-tDCS arm, as this would omit any nonspecific treatment effects (match for attention, expectation) of entering a neurostimulation treatment protocol. This protocol will provide a basis for future studies of tDCS stimulation parameters (frequency, duration, number) that could optimize adherence and treatment effects of drug use outcomes.

In phase two (UH3), we will perform a larger RCT using the same treatment protocol in 100 opioid dependent participants who recently initiated buprenorphine or methadone. Participants will be randomized to receive five sessions of tDCS+CCN priming stimulation vs. sham tDCS+CCN priming. Phase two will address long-term (3-month) neurobehavioral outcomes, including opioid relapse, craving, and sustained fMRI changes during a paradigm that challenges networks associated with craving (CR) and cognitive control (CCN). During the 12 weeks of opioid maintenance treatment, we will examine our primary clinical outcome, relapse (opioid use on >4 days per month and having an opioid positive urine screen), as well as days of opioid use.

2.c Inclusion/Exclusion Criteria:

UG3/UH3 Inclusion Criteria: (a) current opioid dependence, (b) between 21-50 years of age, (c) recent initiation of buprenorphine or methadone (<30 days)

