Exclusion Criteria: (a) diagnosis of organic brain disorder, bipolar disorder, schizophrenia, schizo-affective, schizophreniform, or paranoid disorder, (b) current suicidality, (c) evidence of neurocognitive dysfunction, (d) contraindications for tDCS (e.g seizure disorder), (e) probation/parole requirements or an upcoming move that might interfere with protocol participation, (f) planning to terminate buprenorphine or methadone in less than 3 months, and (g) scalp lesions near the tDCS electrode sites.

Exclusion Criteria related to FMRI scanning are: (a) history of neurological disorder (e.g., epilepsy, stroke, brain injury with loss of consciousness>10 min), (b) impaired uncorrected vision, and (c) MRI contraindications (e.g., claustrophobia, specific metallic implants and injuries, and pregnancy).

tDCS-related considerations: Careful consideration will be given when determining whether tDCS is safe for potential participants. Additional exclusion criteria related to tDCS include: metal implanted in the cranial cavity, pacemaker, poor cognitive functioning (i.e., Alzheimer's disease or dementia), history of neurological disorder (e.g., epilepsy or other seizure disorder), or other significant or chronic medical conditions that affect the brain (e.g., Parkinson's disease, Huntington's disease, multiple sclerosis, traumatic brain injury). [name] will have the final decision regarding whether a participant is medically stable enough to engage in this trial.

2.d Power Calculation and Sample Size:

In the UG3 phase of this project, we plan to enroll 60 participants. With an expected attrition rate of 20% (data loss over two sessions due to poor performance or movement artifact—a conservative estimate that is a larger loss than in our ongoing FIRST study), our final sample size will be 48, or 24 per group. This number provides 82% power for the expected effect size of .75, chosen based on prior tDCS studies and our belief that a large effect size should be required to continue to the UH3. In the UH3 phase, we again anticipate a 20% attrition rate over the 5 tDCS sessions and initial two fMRI scans. If the third scan (at 4 weeks) is missed, we expect this will be due to treatment drop-out or relapse. With 100 participants enrolled, we will have a final sample of 80 patients which provides a power of .8 to detect a group difference in relapse between relapse and sham of 15% vs 39% at 3 months follow-up.

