1) CR: Two 2x2 mixed ANOVAs will be used to determine whether mean response to cues during CR decline across nodes of the craving network (VS, amygdala, VMPFC), including salience network (AI, ACC) and increases in the CCN (MFG, IPL). Significant pre-post main effects and group x treatment interactions are predicted in each. Those who received tDCS+CCN priming are expected to exhibit greater change. Follow up analyses of individual nodes within each network and whole-brain voxel-wise contrasts will be conducted to inform phase 2 analyses.

2) n-Back: Two 2x2 mixed ANOVAs will be used to determine whether mean response to the n-Back challenge increases across nodes of the CCN (MFG, IPL) and the salience network (ACC and AI). Significant pre-post main effects and group x treatment interactions are predicted in each. Those who received tDCS are expected to exhibit greater change. Follow up analyses of individual nodes within each network and whole-brain voxel-wise contrasts will be conducted to inform phase 2 analyses.

3) Resting state: Two 2x2 mixed ANOVAs will be used to determine whether mean network coherence (functional connectivity) decreases across nodes of the craving network (VS, amygdala, VMPFC), including the salience network (AI, ACC) and increases in the CCN (MFG, IPL). Significant pre-post main effects and group x treatment interactions are predicted

in each. Those who received tDCS are expected to exhibit greater change. Parallel exploratory analyses will be conducted to examine resting state functional connectivity of the salience network and DMN.

In the UH3, neuroimaging analyses will generally parallel those described for UG3. We will use a 2x3 ANOVA (three time points) to test the hypothesis that tDCS+CCN priming will be superior to sham tDCS+CCN priming on both subjective and fMRI measures of craving and cognitive control at the end of 5 sessions and at 3-months post tDCS. This same analytical method will be used to test the effect of intervention on days of drug use at the end of 5 sessions and at 3-months. We will use the Pearson χ^2 -test of independence to compare tDCS+CCN priming to sham tDCS+CCN priming on relapse at 3-months.

FMRI data analyses

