EEG outcome measures analyses. We will conduct a repeated-measures ANCOVA with a within-subject factor of time (baseline and end-of-stimulation (EOS)), between-subject factor of intervention condition (active tDCS and sham) and covariates to test if there is a statistically significant difference in in the EEG outcome (Δtheta) across treatment groups. Pearson correlations will be used to examine beta PSD values in relation to craving scores. A separate ANCOVA with the same factors will be used to explore treatment group differences in resting state EEG beta PSD values. Covariates for both analyses will include the baseline measure of the evaluated outcome, as well as baseline variables found to vary significantly ($p < 0.05$) by intervention arm, or which significantly ($p < 0.05$) predict attrition at EOS. Post-hoc t-tests will be used to probe anticipated significant interactions.

5. Quality Assurance

All research personnel, will have formal training in research with human subjects (e.g., CITI training, NIH Human Subjects training). Drs. [name], [name], and [name] will provide training to and supervise research assistants. Research assistants will also have training in Good Clinical Practice.

Drs. [name] and [name] will be responsible for quality control of this study. They will review recruitment and retention reports, and AE reports on a weekly basis. The MPIs (or their designee) will inspect BL documents (consent forms, release of information) for completeness within a week after they are signed. The MPIs (or their designee) will also conduct protocol and data quality monitoring twice a year using a checklist. This monitoring will include reviewing other study records to ensure completeness.

6. Regulatory Issues

6.a, 6.c Reporting of SAEs, Non-Medication Trials

Drs. [name] and [name] will be responsible for overseeing the daily safety of all participants. There are several ways in which they will become aware of adverse events. First, research staff will ask participants about serious adverse events (as defined by Office of Human Research Protections (OHRP); e.g., inpatient hospitalization) at each research contact point (UG3: baseline, week 2 assessment, 5 tDCS appointments, 2 fMRI; UH3: baseline,

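### UH3 relapse power of .8 with 80 analysed is stated without alpha or sidedness; the planned chi-square test at two-sided 5% has about 69%

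*Combined protocol and SAP*

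**What the plan says.** Section 2.d enrols 100 participants in UH3, allows 20% attrition, and concludes: "we will have a final sample of 80 patients which provides a power of .8 to detect a group difference in relapse". The rates follow as "sham of 15% vs 39% at 3 months follow-up". The wording that labels the two arms is garbled; I read 15% as the active arm. No alpha, sidedness or test is given there.

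The test is named in section 4.c, where a Pearson chi-square is specified: "test of independence to compare tDCS+CCN priming to sham tDCS+CCN priming on relapse at 3-months". No level is attached to it. The section 4.c paragraph on EEG outcome measures does use p < 0.05, but for choosing covariates ("as well as baseline variables found to vary significantly" between arms, or predictive of attrition), not for testing relapse.

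Section 2.a, 2.b gives relapse its standing in UH3: "we will examine our primary clinical outcome, relapse".

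Section 2.d handles UG3 in the same way, again without a level: "our final sample size will be 48, or 24 per group", then "This number provides 82% power for the expected effect size of .75".

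**The concern.** A power figure means something only together with the level and sidedness of the test. Here both are missing for the primary clinical outcome, and the stated .8 is not what the planned test delivers at the level most readers would assume. A Pearson chi-square rejects for differences in either direction, so run at 5% it is a two-sided 5% test.

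Two things are at stake. First, the trial may be less able to detect its planned effect than section 2.d implies. Second, without a declared level a borderline result has no fixed reading. With 6/40 versus 13/40 relapses the chi-square p-value is 0.066, a success at 10% and a failure at 5%. The level could then be settled after the data are seen.

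**Working it through.** **Inputs.** From section 2.d: 80 analysed (100 × 0.8), relapse 15% versus 39%, stated power .8. From section 4.c: Pearson chi-square, with no continuity correction mentioned. Assumed because the documents do not say: 1:1 allocation, so n = 40 per arm, and the levels shown below.

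**Formulas.** Difference = 0.39 − 0.15 = 0.24; mean rate = 0.27.

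- Standard error under the null (pooled): SE0 = √(2 × 0.27 × 0.73 / 40) = 0.0993.
- Standard error under the alternative (unpooled): SE1 = √((0.15 × 0.85 + 0.39 × 0.61) / 40) = 0.0956.
- Power, pooled: Φ((0.24 − z × SE0) / SE1).
- Power, unpooled: Φ(0.24 / SE1 − z).
- Exact: sum the binomial probabilities of all 41 × 41 outcomes that the uncorrected Pearson test rejects.

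**Reproducing the plan's .8** (one-sided 5%, equivalently two-sided 10%; z = 1.645):

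- Pooled: Φ((0.24 − 0.1633) / 0.0956) = Φ(0.803) = 0.789.
- Unpooled: Φ(2.511 − 1.645) = Φ(0.866) = 0.807.
- Exact: 0.802.

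**The planned test at two-sided 5%** (z = 1.960):

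- Pooled: Φ((0.24 − 0.1946) / 0.0956) = Φ(0.475) = 0.683.
- Unpooled: Φ(2.511 − 1.960) = Φ(0.551) = 0.709.
- Exact: 0.692.

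| 15% vs 39% | Pooled | Exact Pearson | Unpooled |
|---|---|---|---|
| 40 per arm, two-sided 5% | 0.683 | 0.692 | 0.709 |
| 40 per arm, one-sided 5% / two-sided 10% | 0.789 | 0.802 | 0.807 |
| 50 per arm (all 100 enrolled), two-sided 5% | 0.780 | 0.790 | 0.802 |

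**Level at which 40 per arm gives exactly 80%.** Pooled: z = (0.24 − 0.8416 × 0.0956) / 0.0993 = 1.607, two-sided alpha 0.108. Unpooled: z = 2.511 − 0.8416 = 1.669, two-sided alpha 0.095.

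**Sensitivity.** The uncorrected Pearson test is the favourable reading. At two-sided 5% with 40 per arm, the Yates correction gives 0.597 and Fisher's exact test 0.606. A 2:1 split of the 80 gives 0.60 to 0.66 (pooled), depending on which arm is larger.

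**Detectable difference at two-sided 5%, 80% power, 40 per arm.** 15% versus 43.0% (pooled; exact power at 43% is 0.806), or 15% versus 42.0% (unpooled).

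**Borderline example.** 6/40 versus 13/40: pooled rate 19/80 = 0.2375, z = 0.175 / √(2 × 0.2375 × 0.7625 / 40) = 1.839, two-sided p = 0.066. One more relapse in the sham arm, 6/40 versus 14/40, gives z = 2.066, p = 0.039.

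**UG3 as a consistency check only**, taking .75 as Cohen's d in a two-group t-test (noncentral t). With 24 per group, one-sided 5% gives 0.820 and two-sided 5% gives 0.720. With all 60 enrolled, 30 per group, two-sided 5% gives 0.815. The stated 82% is matched by the first of these.

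**The case against.** The strongest reply is that no level is stated, so .8 cannot contradict one; the 69% depends on a two-sided 5% level that the reader brings. This is right as far as it goes. The omission is what the text shows directly, and the 69% is conditional. It does not rescue the passage: no two-sided 5% calculation with 40 per arm reaches .8, and nothing in the documents declares a one-sided test or a 10% level.

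A second reply is that the origin of .8 is uncertain. Two-sided 5% on all 100 enrolled gives 0.780 to 0.802, nearly as close as one-sided 5% on 80. This also stands in part. But section 2.d attaches .8 to the sample left after attrition. If the enrolled number was used, the attrition allowance never entered the power figure, and 80 analysed still gives about 69%. The text needs correcting on either account.

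Third, the supporting evidence for a one-sided convention is limited. The UG3 match requires .75 to be Cohen's d in an unadjusted comparison. With baseline adjustment and an assumed correlation of 0.45 to 0.5 (not in the documents), two-sided 5% with 24 per group gives about 0.81 to 0.84, which also covers 82%. The directional hypothesis in section 4.c, "to test the hypothesis that tDCS+CCN priming will be superior to sham tDCS+CCN priming on both subjective and fMRI measures", concerns craving, cognitive control and fMRI, not relapse, and a directional hypothesis does not by itself imply a one-sided test. I therefore treat one-sided 5% as the likeliest source of .8, not as established.

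Finally, one-sided 5% and two-sided 10% share the same power here but are not the same rule: a chi-square at 10% can also reject in favour of sham. A declaration has to say which is meant.

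**Conclusion.** The concern holds. Alpha and sidedness are not declared for the primary clinical outcome, and the stated power does not match the planned chi-square test unless a level of about 10% two-sided is used. At two-sided 5% with 80 analysed, power for 15% versus 39% is about 69% (0.68 to 0.71), some 9 to 12 points below the stated .8. The risk of missing that difference is about 31%, compared with the implied 20%.

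This rests on 1:1 allocation, the uncorrected Pearson test and 80 analysed; the 2:1 split and the corrected or exact tests tried at two-sided 5% all lower the figure. Confidence is high in the omission and the conditional arithmetic, and lower in where .8 came from. No separate error is claimed for UG3. It should be fixed before the relapse data are analysed.

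**What to change.** State alpha and sidedness for the relapse test in both 2.d and 4.c, and the allocation ratio in 2.d. Then take one of two routes:

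- **Two-sided 5%.** Restate UH3 power as about 69% for 15% versus 39% with 80 analysed, or give the detectable difference at 80% power as 15% versus about 43%.
- **One-sided 5% or two-sided 10%.** Say so explicitly in both sections, and the .8 can stand. The chi-square need not be replaced. If one-sided is meant, name the direction in which a result counts, since the chi-square alone does not.

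Apply the same declared convention to the UG3 figure of 82%.

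The cost is wording in two sections, with no extra patients and no change of endpoint or test. The first route shows a less favourable power; the second rests the relapse result on a visibly looser error level. For reference, keeping 80% power at two-sided 5% for the same rates would take 53 per arm by the pooled formula: 106 analysed, and 106 / 0.8 = 132.5, so 133 enrolled (134 for equal arms). The correction proposed here does not require that.

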week 2, 4, 6, 8, 12 assessments, 5 tDCS appointments, 3 FMRI). For monitoring expected adverse effects of tDCS, we use the SAFTEE at each session that includes changes in physical health status. Deaths are reported by significant others when we try to locate participants who missed appointments. Butler Hospital has a psychiatric emergency room available 24 hours a day. All research procedures will be supervised by Drs. [name] and [name] who will be on call 24-hours a day.

Second, all study staff will be trained in the OHRP definitions of adverse events that are also unanticipated problems; serious adverse events; or unanticipated problems that are not adverse events. All study staff are required to report any event that might meet one of these criteria to one of the PIs immediately both verbally and in writing. When necessary, a report of a serious adverse event will result in one of the PIs contacting the participant to further assess the event.

Drs. [name] and [name] will meet weekly with research assistants to review staff experiences with participants. Based on the sources of information detailed above as well as direct patient contact and/or consultation with the scientific team, Drs. [name] and [name] will determine if the event is: a) a serious adverse event that is also an unanticipated problem; b) an unanticipated problem that is not an adverse event. The Butler Hospital IRB require that fatalities related to the study be reported within 24 hours, all other serious adverse events related to the study be reported within 5 business/7 calendar days, and other serious adverse events related to the study be reported at the continuing review (at least annually).

6.d Reporting of IRB Actions to NIDA

All SAEs will be reported to NIDA within 72 hours of the MPIs becoming aware.

6.e Report of changes of amendments to the protocol

Changes to the proposal must be approved by NIDA prior to implementation

6.f Trial stopping rules

This study will be stopped prior to its completion if: (1) the intervention is associated with adverse effects that call into question the safety of the intervention; (2) any new information becomes available during the trial that necessitates stopping the trial; or

6.g Disclosure of Conflict of Interest

[name]: None

[name]: None

[name]: None

[name]: None

7. Trial Safety

7.a Potential Risks and Benefits for Participants

Potential Coercion.

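### UH3 craving and cognitive-control measures: the 2x3 ANOVA has no rule for a missed third visit; a baseline-adjusted model using all data would keep the end-of-session data and be more precise

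*Combined protocol and SAP*

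**What the plan says.** Section 4.c (Data Analysis Plan) introduces the UH3 imaging work with "In the UH3, neuroimaging analyses will generally parallel those described for UG3" and then names one test: "We will use a 2x3 ANOVA (three time points) to test the hypothesis that tDCS+CCN priming will be superior". It covers subjective and fMRI measures of craving and cognitive control, at the end of the five sessions and at 3 months. Section 4.c then extends it: "This same analytical method will be used to test the effect of intervention on days of drug use".

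Section 2.d (Power Calculation and Sample Size) deals with loss to follow-up. For UH3, "we again anticipate a 20% attrition rate over the 5 tDCS sessions and initial two fMRI scans", which takes 100 enrolled to 80. On the third scan it says only: "If the third scan (at 4 weeks) is missed, we expect this will be due to treatment drop-out or relapse". It gives no rate for that loss and no analysis rule.

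The timing is inconsistent. Section 2.d puts the third scan at 4 weeks. Section 2.a/2.b says "Phase two will address long-term (3-month) neurobehavioral outcomes, including opioid relapse, craving, and sustained fMRI changes", and section 4.c also tests the fMRI measures at 3 months. The list of UH3 contacts in section 6.a/6.c reads "week 2, 4, 6, 8, 12 assessments, 5 tDCS appointments, 3 FMRI" and does not say when the scans fall.

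Baseline adjustment appears elsewhere in the plan: for craving in the UG3 go/no-go rule (section 2.a/2.b), and for the EEG outcomes, which are also adjusted for predictors of attrition (section 4.c). For the fMRI models, the only covariate named is type of substance used.

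**The concern.** A conventional repeated-measures ANOVA needs all three measurements. Someone who completes the sessions and the first two scans but misses the third visit leaves the analysis altogether, so a valid end-of-session comparison loses data because of a later event. By the plan's own account that event is likely to be drop-out or relapse. The loss may therefore be related to outcome. It may also be unequal by arm, because the trial is planned on relapse being more common under sham.

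Two things are at stake. The first is precision at end of sessions. The second is bias: if those doing worse are removed and sham loses more of them, the remaining sham group looks too good and a true benefit of active stimulation is understated.

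**Working it through.** **The plan's own figure.** The plan gives no power figure for these measures. Its only UH3 figure is 0.80 for relapse, "a group difference in relapse between relapse and sham of 15% vs 39% at 3 months follow-up", with 80 people. At 40 per arm this comes to 0.79 one-sided at 5% and 0.68 two-sided. That is a separate matter and is not used below.

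**Inputs.** From section 2.d: 80 people after attrition, and planned 3-month relapse of 15% and 39%. Assumed, because the documents do not give them: 1:1 allocation (40 per arm), two-sided 5%, effect 0.5 SD, SD 1, and baseline to end-of-session correlation r of 0.3, 0.5 or 0.7. Third-visit loss is taken as all, half, a quarter or none of the planned 3-month relapsers.

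**Numbers kept (active/sham).**
- All lost: 40 × 0.85 = 34 and 40 × 0.61 ≈ 24, total 58.
- Half: 40 × 0.925 = 37 and 40 × 0.805 ≈ 32, total 69.
- A quarter: 40 × 0.9625 = 38.5 and 40 × 0.9025 ≈ 36, total about 74.5.
- None: 40 and 40.

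**Formulas.** The group-by-time contrast of the ANOVA at end of sessions is a difference in change from baseline, with SE = √[2(1 − r)(1/nA + 1/nS)]. With everyone kept and baseline as covariate, SE = √[(1 − r²)(2/40)]. Power is from the noncentral t distribution. For r = 0.5 with 58 kept, SE = √[1 × (1/34 + 1/24)] = 0.27. With 80 kept and adjusted, SE = √(0.75 × 0.05) = 0.19.

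| End-of-session analysis | Power at r = 0.3 | 0.5 | 0.7 |
|---|---|---|---|
| ANOVA, 58 kept | 34% | 45% | 66% |
| ANOVA, 69 kept | 41% | 53% | 75% |
| ANOVA, about 74.5 kept | 44% | 57% | 78% |
| ANOVA, 80 kept | 46% | 60% | 81% |
| 80 kept, baseline-adjusted | 64% | 72% | 87% |

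From unrounded values, retention is worth 12/14/15 points in the upper case, 6/7/6 at half and 3/3/3 at a quarter. Baseline adjustment is worth a further 18/12/6 points. With equal numbers, its variance ratio is (1 − r²)/[2(1 − r)] = (1 + r)/2, that is 0.65, 0.75 and 0.85, so it helps at any r below 1.

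**Cross-check with a flat loss rate.** With r = 0.5 and 20% of each arm missing the third visit, the ANOVA uses 32 per arm, with SE 0.250 at both visits. The all-data model has SE 0.194 at end of sessions and 0.214 at the third visit. With 10–30% missing and r of 0.3–0.7, the variance ratio is 0.46–0.76 at end of sessions and 0.64–0.84 at the third visit.

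**Bias, by simulation.** There were 10,000 trials per scenario, 40 per arm, with an effect of 0.50 or 0 SD at both visits. Baseline/end-of-session, baseline/third and end-of-session/third correlations were 0.3/0.3/0.5, 0.5/0.4/0.7 or 0.7/0.6/0.8. Third-visit loss was random or fell on people with worse values, driven by either the end-of-session value or the unseen third value. Loss in sham and active was 39% vs 15%, half of that, or 27% in both.

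- Random loss, or loss equal by arm: both methods give 0.49–0.51 for a true 0.50.
- Unequal, outcome-related loss, true effect 0.50: over both visits and both mechanisms the completer ANOVA gives about 0.32–0.49 at full loss and 0.41–0.49 at half. The low end also occurs at end of sessions, where the all-data model gives 0.50 in every case.
- Same loss, no true effect: the completer estimate shifts against the active arm by 0.02–0.18 (half loss: 0.01–0.10), with two-sided rejection of 5–9%.
- Third visit: the all-data model gives 0.50 only if observed values explain the loss. If loss depends on the unseen third value, it gives 0.31–0.45 against 0.32–0.45 for the ANOVA (half loss: 0.40–0.47 against 0.41–0.47), with false-positive rates of 6–13% against 6–9%.

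**The case against.** The strongest reply is that deletion of incomplete cases is inferred. The plan does not write it, and since UH3 imaging is broadly to follow UG3, a two-time-point analysis to end of sessions could also be run and would keep everyone with two scans. That stands as a limit. But the 2x3 ANOVA is the test named for the UH3 hypothesis, and a reader cannot tell who is in it.

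Second, the upper case needs every 3-month relapser to miss the third scan, although the only passage on a missed third scan places it at 4 weeks. Loss could be far smaller, and at a quarter of relapsers retention is worth only about 3 points. This also stands. In the smaller-loss cases, most of the gain comes from baseline adjustment at r of 0.3 or 0.5; at 0.7 and half loss the two are about equal. A mixed ANOVA without that adjustment is still valid.

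Third, the replacement does not cure loss that depends on the unseen third value, which is plausible given the expected causes. That is correct and is why a sensitivity analysis is needed.

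Fourth, the error runs against the active arm. In a separate simulation, false claims of benefit were 0.4–2.5%, no higher than the nominal 2.5%. So the risk is a missed or understated benefit, not a spurious one.

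Finally, the week 2–12 assessments are listed separately from the scans, so a missed scan need not mean missing craving data. The document does not say where craving is collected.

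**Conclusion.** The point holds. The plan names a complete-data method, expects outcome-related loss at the third visit beyond its attrition allowance, and gives no rule for it. The direction is firm: an all-data, baseline-adjusted model is more precise at end of sessions for any correlation below 1, even with no missed visits. It also removes end-of-session bias in every simulated scenario.

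The size is not firm. It rests on the assumed effect, correlation and loss, and the loss depends on when the third scan takes place, which the document leaves in conflict. At r = 0.5, end-of-session power rises to 72% from between 45% and 60%. At the third visit the model gains precision, but it removes bias only if observed data explain the loss. The primary relapse chi-square test is untouched. The change should be made, but it does not threaten the trial's main conclusion.

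**What to change.** - For the UH3 fMRI, craving and cognitive-control measures, replace the 2x3 ANOVA with a likelihood-based repeated-measures model of the two post-baseline visits. Use all available data, baseline as covariate, and a group contrast at each visit.
- Add a third-visit sensitivity analysis for loss that depends on unseen values, for example an arm-specific delta adjustment taken to a tipping point. Report third-visit loss with reasons by arm.
- Reconcile the third scan at 4 weeks (section 2.d) with the 3-month fMRI time point (sections 2.a/2.b and 4.c).
- Days of use is a count. If the week 2–12 assessments collect it, analyse it with a count model, such as negative binomial with days covered as offset, and check that the model is reasonable given that days used cannot exceed days covered.
- Optional, for precision only: analyse the UG3 fMRI outcomes by ANCOVA on baseline.

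The cost is SAP wording and a little more analysis, with no new data. The downside is that the main model assumes observed data explain third-visit loss. If they do not, its third-visit estimate is about as biased as the ANOVA's but has a smaller standard error, so the sensitivity analysis must accompany it.
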